## SCHEDULE OF ACTIVITIES

The Schedule of Activities table provides an overview of the protocol visits and procedures. Refer to **STUDY PROCEDURES** and **ASSESSMENTS** sections of the protocol for detailed information on each procedure and assessment required for compliance with the protocol.

The investigator may schedule visits (unplanned visits) in addition to those listed in the Schedule of Activities table, in order to conduct evaluations or assessments required to protect the well-being of the patient.

Visit Identifiers	Screening Day -45 to Day 1	Enrollment	
		Biospecimen Collection Day 1	Post-Biospecimen Follow-up ≤30 days after receipt of NGS results at the provider's facility
Informed Consent 	X		
Preliminary eligibility assessment 	X		
Archival tumor tissue assessment 	X		
Confirmation of eligibility 	X		
Additional medical and oncological history 		X	
Archival tumor tissue submission 		X	
Procedures			
De novo tumor biopsy 		X	
Research blood collection 		X	
a. circulating free (cf) DNA sequence analysis; b. germline DNA sequence analysis; c. translational analyses.			
Pregnancy test 	X	X	X
Clinical Assessments			
Adverse events monitoring 		X	X
NGS results consultation 			X
Other Assessments			
CCI CCI			C C
Record next anti-cancer treatment following de novo biopsy 			X

cf = circulating free; DNA=deoxyribonucleic acid; NGS = Next generation sequencing.

1. **Informed Consent:** Study consent is obtained before undergoing study-related activities and should be provided as close as possible to the day of biospecimen collection, optimally the day of, but no more than 45 days before the *de novo* tumor biopsy or research blood collection
2. **Preliminary Eligibility Assessment:** Confirmation of demographics, histological diagnosis, prior systemic anti-cancer therapy regimens (and discontinuation reasons, if appropriate) or radiation therapy. Patients who have started new anti-cancer therapy **prior** to performing the *de novo* tumor tissue biopsy or research blood collection are not eligible and should be discontinued from the study. Screen failures are defined as participants who consent to participate in the clinical study but do not subsequently undergo biospecimen collection (ie, *de novo* tumor biopsy and research blood collection are not performed).

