8. **Research blood collection:** Research blood collection may be performed at a separate visit (which may be a home visit, if appropriate) to the *de novo* tumor tissue biopsy but must occur  $\leq$ 5 days before or  $\leq$ 1 day (24 hours) after the *de novo* biopsy. Please refer to the laboratory manual for detailed instructions. See [Section 8](#) for details. Research blood specimens must be shipped no later than one week after collection. Please refer to the laboratory manual for detailed collection, processing, storage, and shipment instructions.
9. **Pregnancy Test:** Specific only to Austria. Monthly pregnancy tests per institutional guidelines.
10. **Adverse event monitoring:** Adverse event collection will begin at the time of the *de novo* tumor biopsy and research blood collection, whichever occurs first, through and including 24 hours post-biospecimen collection.
11. **NGS results consultation:** NGS consultation will occur within 30 days of receipt of the *de novo* tumor biopsy or cfDNA NGS results at the provider's facility. These visits should preferably be conducted in person, although phone visits are permitted if the patient is unable or unwilling to travel to the facility.

CCI

CCI

14. **Next anti-cancer therapy decision:** Next anti-cancer medication following *de novo* tumor biopsy or cfDNA sample collection and whether impacted by the NGS results will be recorded in the appropriate CRF page.

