## 1.2. Potential Risks and Possible Benefits

The primary potential risk to patients who participate in the study is associated with the *de novo* tumor biopsy performed as a study-related procedure. To be eligible for the study patients must have a tumor lesion that is considered to be safely accessible to a *de novo* biopsy performed in accord with local institutional practice standards. See [Section 4](#) for details.

Possible benefits for patients who participate in the study derive from the NGS results from the analysis of their tumor tissue and/or blood performed by a third-party laboratory. These results are returned to the patient's physician/ health care provider who will then discuss the results with the patient. To enable sufficient time to thoroughly discuss the results and possible treatment implications, the study also supports the direct interaction between the patient and the physician by incorporating dedicated consultation time (See [Schedule of Activities](#)). Further, patients will be able to obtain a personal copy of the NGS results through their health care provider. It is recognized that results from NGS analysis of the patient's tumor tissue and/or blood may not directly impact the subsequent treatment plan. However, only by performing such analyses can low probability treatment opportunities be identified.

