#### **4.2. Exclusion Criteria**

Patients with any of the following characteristics/conditions will not be included in the study:

1. Discontinuation of current or most recent anti-cancer therapy due to toxicity and not progressive disease.
2. Initiation of new anti-cancer therapy after PD prior to planned biopsy.
3. Any medical condition that, in the investigator's judgement, unacceptably increases risk associated with the tumor biopsy or blood sampling procedures (eg, evidence of inadequate wound healing, significant neutropenia or thrombocytopenia, recent history of clinically significant bleeding or tumor hemorrhage).
4. Cohorts 1, 2 and 3 (NSCLC monotherapy, NSCLC combination, RCC with clear cell component) only: Treatment with an anti-PD-1/-L1 agent prior to current or most recent anti-PD-1/-L1 therapy.
5. Cohort 4 (HR+ HER2- breast cancer) only: Treatment with a CDK 4/6 inhibitor prior to current or most recent CDK 4/6 inhibitor.
6. Cohort 5 (castrate-resistant prostate cancer) only: Treatment with an agent that blocks adrenal androgen synthesis (eg, abiraterone acetate) and a second-generation AR antagonist other than enzalutamide (eg, apalutamide).
7. Patients who are investigator site staff members directly involved in the conduct of the study and their family members, site staff members otherwise supervised by the investigator, or patients who are Pfizer employees, including their family members, directly involved in the conduct of the study.
8. Other acute or chronic medical or psychiatric condition including recent (within the past year) or active suicidal ideation or behavior or laboratory abnormality that may increase the risk associated with study participation or may interfere with the interpretation of study results and, in the judgment of the Investigator, would make the patient inappropriate for entry into this study.
9. Austria only: Pregnant female patients; breastfeeding female patients.

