## **7. SAFETY**

### **7.1. Adverse Events**

An AE is defined as any untoward medical occurrence and can therefore be any unfavorable and unintended sign (including an abnormal laboratory finding), symptom, or disease, whether or not related to the patient's participation in the study.

Any AE that occurs from the time the patient undergoes the tumor biopsy and research blood collection, whichever occurs first, through and including 24 hours post tumor biopsy and blood collection must be recorded. The investigator is required to assess whether the AE may be related to the patient's participation in the study.

The investigator must pursue and obtain information adequate to determine the outcome of the AE and to assess whether it meets the criteria for classification as a research related injury requiring immediate notification to Pfizer as described below.

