#### **7.1.1. Research Related Injury**

Should a patient, in the investigator's opinion, suffer a medically important research related injury caused by their participation in the study, the designated Pfizer clinician or medical monitor must be notified immediately by emailing [CCI](#) [REDACTED]

A medically important research related injury is any untoward medical occurrence that:

- Results in death;
- Is life-threatening (immediate risk of death);
- Requires inpatient hospitalization or prolongation of existing hospitalization;
- Results in persistent or significant disability/incapacity (substantial disruption of the ability to conduct normal life functions);
- Results in congenital anomaly/birth defect.

Medical and scientific judgment is exercised in determining whether an injury is an important medical event. An important medical event may not be immediately life-threatening and/or result in death or hospitalization. However, if it is determined that the event may jeopardize the patient or may require intervention to prevent one of the other outcomes listed in the definition above, the important medical event should be reported as a research related injury.

An investigator may be requested by the designated Pfizer clinician or medical monitor to obtain specific additional follow-up information in an expedited fashion. In general, this will include a description of the injury in sufficient detail to allow for a complete medical assessment of the case and independent determination of possible causality. Information on other possible causes of the event, such as concomitant treatments, vaccines, and/or illnesses must be provided. In the case of a patient death, a summary of available autopsy findings must be submitted as soon as possible to Pfizer or its designated representative.

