8.3. Analysis of Safety Data

Formal statistical analysis, eg, statistical testing, will not be performed on the safety data. However, descriptive statistics will be generated for adverse events in the SA population.

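### Procedure-related events that start after the roughly 24-hour recording window need not reach the only planned safety summary, and the protocol's own safety passages disagree about that window

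*Protocol*

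**What the plan says.** Protocol Section 7.1 opens the recording period at the biopsy or the blood collection, whichever comes first, and closes it on a clock: events "through and including 24 hours post tumor biopsy and blood collection must be recorded". Footnote 10 of the Schedule of Activities gives the same end, "through and including 24 hours post-biospecimen collection". The row that carries this footnote, "Adverse events monitoring", is nevertheless marked both on Day 1 and at the post-biospecimen follow-up, which falls up to 30 days after the sequencing results reach the provider.

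For each adverse event, Section 7.1 asks the investigator to establish the outcome and to "assess whether it meets the criteria for classification as a research related injury requiring immediate notification to Pfizer". Section 7.1.1 then requires immediate notification if a patient should "suffer a medically important research related injury caused by their participation in the study". It lists the seriousness criteria and states no end date.

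On analysis, Protocol Section 8.4 plans no formal safety analysis. SAP Section 8.3 also excludes formal testing but adds that "descriptive statistics will be generated for adverse events in the SA population". Neither section mentions research related injuries.

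**The concern.** The study gives no investigational product. Protocol Section 1.2 identifies the study biopsy as the main risk of taking part, and Sections 4.1 and 5.2.1.2 allow excisional as well as core needle biopsies. The adverse event summary is the only place where the study plans to report what those procedures did to patients.

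The passages feeding that summary do not share one time frame. Required recording closes after a day or two, injury notification has no stated close, and the visit schedule suggests that adverse events are still being asked about weeks later. Events judged to be caused by the procedure but starting after the window can therefore be absent from the summary even when every site follows the text. Sites that read the schedule row differently from its footnote will also contribute unequal data. The primary genomic results are not affected. At stake is whether the safety summary is complete and consistent across sites.

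**Working it through.** The plan states no figure on this point, so the check sets the passages side by side. The only arithmetic is the length of the window.

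**Length of the window after the biopsy.** Section 7.1 closes 24 hours after biopsy and blood collection. Section 5.2.1.3 and footnote 8 allow blood from 5 days before to 24 hours after the biopsy.

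- Blood drawn before or with the biopsy: recording closes 0 + 24 = 24 hours after the biopsy.
- Blood drawn at the latest permitted time: recording closes 24 + 24 = 48 hours after the biopsy.

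Required recording therefore ends one to two days after the biopsy, depending on when the blood was drawn.

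**Time frame of each passage.**

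| Source | Events covered | Stated end |
|---|---|---|
| Protocol 7.1 | all adverse events | 24 hours after biopsy and blood collection |
| Schedule of Activities, footnote 10 | all adverse events | 24 hours after biospecimen collection |
| Schedule of Activities, adverse event row | all adverse events | marked at the follow-up visit |
| Protocol 7.1.1 | medically important injuries caused by participation | none stated |
| SAP 8.3 | adverse events in the SA population | none stated; no rule for injuries |

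**Three illustrative events, followed through the text.**

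1. *Onset 10 hours after the biopsy.* Recorded under 7.1, assessed for injury classification, and summarised under SAP 8.3. All passages agree.
2. *Hospital admission for a new event on day 4 after the biopsy, judged caused by it.* Section 7.1 and footnote 10 do not require a record. Section 7.1.1, on its own wording, requires notification. The schedule row suggests the site will still be asking about adverse events at follow-up, while its footnote says collection has ended. SAP 8.3 counts the event only if someone entered it as an adverse event, and no passage requires that.
3. *A non-serious event on day 4, judged related.* Section 7.1 does not require a record. Section 7.1.1 does not apply unless the event is medically important. It reaches SAP 8.3 only if a site chooses to record it.

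Cases 2 and 3 show the gap. That such events would be left out follows from the silence of Section 7.1.1 and SAP 8.3; no passage states it outright.

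**The case against.** **Later recording is not forbidden.** Section 7.1 defines an adverse event without a time limit and says what must be recorded. A site working from the schedule row could properly record a later event. This stands: a reader might infer that late events cannot be recorded, but the text supports only that they are not required to be. The same row, set against its footnote, is also the clearest sign that the passages need reconciling.

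**Section 7.1.1 may not be open-ended.** It sits under 7.1, and 7.1 feeds adverse events into it, so it could be read as covering only events inside the window. That reading is possible. It would make the two rules agree, but a late serious injury would then be neither recorded nor notified. Its own text sets no such limit, and one criterion, congenital anomaly, could hardly arise within a day or two. Either way the scope needs stating.

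**Injury reports need not be lost.** Section 7.1.1 lets the sponsor request expedited follow-up information, and Section 10.2 has safety reporting forms retained. The case report form is not available here. A reader might infer that the two sources could never be reconciled. The documents do not support that: the sponsor could merge them, but no rule says that it will.

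**Late harms are not named as such.** Exclusion criterion 3 lists "evidence of inadequate wound healing, significant neutropenia or thrombocytopenia, recent history of clinically significant bleeding or tumor hemorrhage" as examples of conditions that may unacceptably raise procedural risk. A reader might take this as the protocol naming delayed harms, or conclude that biopsy harms usually appear after the first day. The list describes pre-existing conditions, and nothing in the documents gives the timing of complications.

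**A short window is sensible.** In advanced cancer, longer all-cause collection would mostly gather background illness. Safety is neither an objective nor an endpoint among those shown in Protocol Section 2. Both points are fair; they support keeping the all-cause window and treating this as a matter of completeness.

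**Conclusion.** The point holds in a limited form. Required recording ends about 24 to 48 hours after the biopsy, notification of medically important injuries has no stated end, the schedule row conflicts with its footnote, and SAP Section 8.3 has no rule for including notified injuries. A procedure-related event that starts after the window is not required to appear in the only planned safety summary, and sites may record differently.

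The size is unknown. A reader might try to estimate it by applying an assumed complication rate and an assumed late-onset share to 500 patients. The documents give neither rate. Moreover, the 500 in Protocol Section 3 counts evaluable patients, whereas SAP Section 5.1 defines the SA population as enrolled patients who had a biopsy procedure or a research blood draw. Any percentage understatement obtained this way would only restate the assumed late share.

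The conclusion assumes that sites and analysts follow the text as written and that no case report form instruction or other document already closes the gap.

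**What to change.** Reconcile the adverse event row and footnote 10 of the Schedule of Activities, Protocol Sections 7.1 and 7.1.1, and SAP Section 8.3.

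- **Protocol 7.1 and footnote 10.** Keep the short window for all-cause adverse events. State that two further groups are entered on the adverse event form: later-onset events that the investigator judges related to study procedures and that are reported by the scheduled follow-up contact; and every research related injury under 7.1.1, whatever its onset. The mark at the follow-up visit then has a defined meaning.
- **Protocol 7.1.1.** Say explicitly whether notification depends on the recording window.
- **SAP 8.3.** List study-related adverse events and research related injuries separately, by onset within or after the window.

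The cost is wording in these places and use of the adverse event form at a contact that is already scheduled, which Section 5.3.1 allows by phone. All-cause collection is not lengthened. There are two downsides. The reported event rate may be slightly higher. Attribution is also harder once the next anti-cancer therapy has started, or where the patient is in a concurrent interventional trial, which Section 5.1.2 permits with prior sponsor agreement. Showing onset relative to the window lets readers weigh the later events accordingly.

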#### **7.1.1. Research Related Injury**

Should a patient, in the investigator's opinion, suffer a medically important research related injury caused by their participation in the study, the designated Pfizer clinician or medical monitor must be notified immediately by emailing [CCI](#) [REDACTED]

A medically important research related injury is any untoward medical occurrence that:

- Results in death;
- Is life-threatening (immediate risk of death);
- Requires inpatient hospitalization or prolongation of existing hospitalization;
- Results in persistent or significant disability/incapacity (substantial disruption of the ability to conduct normal life functions);
- Results in congenital anomaly/birth defect.

Medical and scientific judgment is exercised in determining whether an injury is an important medical event. An important medical event may not be immediately life-threatening and/or result in death or hospitalization. However, if it is determined that the event may jeopardize the patient or may require intervention to prevent one of the other outcomes listed in the definition above, the important medical event should be reported as a research related injury.

An investigator may be requested by the designated Pfizer clinician or medical monitor to obtain specific additional follow-up information in an expedited fashion. In general, this will include a description of the injury in sufficient detail to allow for a complete medical assessment of the case and independent determination of possible causality. Information on other possible causes of the event, such as concomitant treatments, vaccines, and/or illnesses must be provided. In the case of a patient death, a summary of available autopsy findings must be submitted as soon as possible to Pfizer or its designated representative.

## **8. DATA ANALYSIS/STATISTICAL METHODS**

Detailed methodology for summary and statistical analyses of the data collected in this study will be documented in a statistical analysis plan (SAP), which will be maintained by Pfizer.

This document may modify the plans outlined in the protocol; however, any major modifications of the primary endpoint and/or its analysis will also be reflected in a protocol amendment.

### **8.1. Analysis Population**

All the endpoints will be analyzed in the evaluable population. The evaluable population is defined as the patients who have both archival tumor tissue and *de novo* tumor biopsy that is sufficient to enable the intended sample analyses.

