## 2. STUDY OBJECTIVES AND ENDPOINTS

Primary Objective:	Primary Endpoint:

To obtain and analyze archival pre-treatment tumor samples and post-progression tumor biopsies to identify molecular markers of resistance to selected anti-cancer therapies.

	

Change in the frequency of gene alterations between pre-treatment tumor samples and post-progression tumor biopsies.

Secondary Objectives:	Secondary Endpoints:

To evaluate the success rate in obtaining paired archival and post-progression tumor biopsies that are adequate to meet the objectives of the study;

To determine concordance in gene alterations identified by NGS analysis of post-progression tumor tissue and blood.

	

Proportion of patients with fully evaluable archival and post-progression tumor biopsy (eg, sample sufficient for all intended analyses at all measured time points);

Overall agreement rates of gene alterations between post-progression biopsy tissue and blood NGS results.

Secondary Objectives by Target Biology:	Secondary Endpoints by Target Biology:

PD-1-L1 inhibition:
 
 
To evaluate alterations in genes encoding HLA, <math>\beta</math>2-Microglobulin, Signal transducer and activator of transcription 1(STAT1), JAK1, JAK2, IFN-<math>\gamma</math>, and interferon-gamma receptor (IFNGR) as mechanisms of resistance to PD-1/PD-L1 checkpoint blockade.
 
	
 
Change in the frequency of alterations in genes encoding HLA, <math>\beta</math>2-Microglobulin, STAT1, JAK1, JAK2, IFN-<math>\gamma</math> and IFN-<math>\gamma</math>R between pre-treatment archival and post-progression samples;
 
The frequency of alterations in genes encoding HLA, <math>\beta</math>2-Microglobulin, STAT1, JAK1, JAK2, IFN-<math>\gamma</math> and IFNGR in cfDNA.
 

CDK4/6 inhibition:
 
 
To evaluate alterations in the Rb gene as a mechanism of resistance to palbociclib.
 
	
 
Change in the frequency of RB1 gene alterations between pre-treatment archival and post-progression samples.
 
The frequency of RB1 gene alterations in cfDNA.
 

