#### 8.5.2. Analysis of Secondary Endpoints

Summary statistics will be generated for the secondary endpoints. For the proportion of patients with fully evaluable archival and post-progression tumor biopsies, proportions and 95% CI will be calculated. For the overall agreement rates of gene alterations between post-progression biopsy tissue and blood NGS results, the frequency of mutations detected from post-progression biopsy tissue, blood and the corresponding 95% CIs will be generated. The concordance between both matched tissue biopsy tissue and blood samples and the 95% CI will also be calculated to evaluate the agreement.

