6. ENDPOINTS AND COVARIATES

6.1. Endpoints

Table 2 Primary, Secondary and Exploratory Endpoints

| |
|--|
| Primary Endpoint: |
| 
 Change in the frequency of gene alterations between pre-treatment tumor samples and post-progression tumor biopsies. |
| Secondary Endpoints: |
| 
 Proportion of patients with fully evaluable archival and post-progression tumor biopsy (eg, sample sufficient for all intended analyses at all measured time points); Overall agreement rates of gene alterations between post-progression biopsy tissue and blood NGS results. |
| Secondary Endpoints by Target Biology:* |
| PD-1/L1 inhibition: |
| 
 Change in the frequency of alterations in genes encoding HLA, β2-Microglobulin, STAT1, JAK1, JAK2, IFN-γ and IFN-γR between pre-treatment archival and post-progression samples; The frequency of alterations in genes encoding HLA, β2-Microglobulin, STAT1, JAK1, JAK2, IFN-γ and IFNGR in cfDNA. |
| CDK4/6 inhibition: |
| 
 Change in the frequency of RB1 gene alterations between pre-treatment archival and post-progression samples. The frequency of RB1 gene alterations in cfDNA and tumor tissue. |
| AR inhibition: |
| 
 Change in the frequency of AR gene alterations between pre-treatment archival and post-progression samples; The frequency of AR gene alterations in cfDNA and tumor tissue; Changes in the expression of nuclear hormone receptors or related RNA signatures reflecting nuclear receptor pathway activity between pre-treatment archival and post-progression samples. |
| PARP inhibition: |
| 
 Change in the frequency of somatic reversion alterations in gBRCA mutant allele between pre-treatment archival and post-progression samples. |
| CCI |
|  |

*All abbreviations are explained in the Appendix 1 of study protocol.

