8.2.2. Analysis of Secondary Endpoints

Summary statistics will be generated for the secondary endpoints. For the proportion of patients with fully evaluable archival and post progression tumor biopsies, proportions and 95% CI will be calculated using the method described in [Section 8.1.2](#). For the overall agreement rates of gene mutations between post progression biopsy tissue and blood NGS results, basic summary statistics such as mean, median, and range of count of alterations per patient across all patients will be generated for each cohort. In addition, mean and median count of alterations in agreement between biopsy and blood samples will be calculated for each cohort. The frequency of alterations detected from post progression biopsy tissue, blood and the corresponding 95% CIs will be generated. In the BE (TBD) and BET (TBD) population, the concordance between both matched biopsy tissue and blood samples and the 95% CI and Cohen's Kappa will also be calculated to evaluate the agreement.

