8.2.3. Analysis of Asset Specific Secondary Ednpoints

Methods described in [Section 8.1.2](#) will be used for the analyses defined in the table below on the BET (TTD) and BET (WETD) population.

Table 3 Analysis Methods for Secondary Endpoints by Target Biology

| Target Biology | Secondary Endpoints | Analysis Methods |
|-----------------------------|--|--|
| PD-1-L1 inhibition | 
 • Change in the frequency of alterations in genes encoding HLA, $\beta 2$-Microglobulin, STAT1, JAK1, JAK2, IFN-γ and IFNGR between pre-treatment archival and post-progression samples. • The frequency of alterations in genes encoding HLA. • $\beta 2$-Microglobulin, STAT1, JAK1, JAK2, IFN-γ and IFNGR. • in cfDNA. | 
 • For each alteration, the estimate of the frequency and the 95% CI at pre-treatment archival and post-progression will be generated; A score based 95% CI will be generated for the difference in frequency between pre-treatment archival and post-progression samples. • For each alteration in cfDNA, the estimate of the frequency and the 95% CI will be generated. |
| • CDK4/6 inhibition. | 
 • Change in the frequency of RB1 gene alterations between pre-treatment archival and post-progression samples. • The frequency of RB1 gene alterations in cfDNA, and tumor tissue. | 
 • For each alteration, the estimate of the frequency and the 95% CI at pre-treatment archival and post-progression will be generated. A score based 95% CI will be generated for the difference in frequency between pre-treatment archival and post-progression samples. • For each alteration in cfDNA, the estimate of the frequency and the 95% CI will be generated. |

| | | |
|---|--|---|

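### The success-rate endpoint for paired biopsies is placed in the evaluable population, which is essentially its own numerator, and no other denominator is named

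*Protocol*

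**What the plan says.** Protocol 2 lists as its first secondary objective: "To evaluate the success rate in obtaining paired archival and post-progression tumor biopsies that are adequate to meet the objectives of the study". The matching endpoint is: "Proportion of patients with fully evaluable archival and post-progression tumor biopsy (eg, sample sufficient for all intended analyses at all measured time points" (the closing bracket is cut here). SAP 6.1 repeats it with the same explanation, "sample sufficient for all intended analyses at all measured time points".

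Protocol 8.1 sets one analysis population without exception: "All the endpoints will be analyzed in the evaluable population". Members must have archival tissue and a de novo biopsy that are adequate for the planned assays. Protocol 3 gives the same definition, and cohort sizes are counted in such patients.

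On the analysis itself, Protocol 8.5.2 says: "For the proportion of patients with fully evaluable archival and post-progression tumor biopsies, proportions and 95% CI will be calculated". SAP 8.2.2 says: "For the proportion of patients with fully evaluable archival and post progression tumor biopsies, proportions and 95% CI will be calculated", and points to SAP 8.1.2, where the one-sample method is the Wilson score interval. Neither section gives a population for this endpoint.

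The SAP does name populations elsewhere. For tissue-blood agreement: "In the BE (TBD) and BET (TBD) population, the concordance between both matched biopsy tissue and blood samples". For the target-specific endpoints, the methods of SAP 8.1.2 "will be used for the analyses defined in the table below on the BET (TTD) and BET (WETD) population". SAP 8.2.1 names populations for the primary endpoint. SAP 8.3 and 8.4 use the SA population for adverse events and for baseline data.

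**The concern.** A success rate needs the failures in its denominator. Protocol 8.1 admits a patient to the denominator only if the pair is adequate, and the endpoint then counts patients whose pair is adequate. The two conditions are nearly the same, so the proportion cannot show how often an adequate pair was obtained.

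At stake is one listed secondary endpoint. A figure at or near 100% could be read as a feasibility result for paired biopsies when it only restates the entry rule. The SAP may modify the protocol (opening of Protocol 8; SAP 2), but for this endpoint it is silent, so the rule in Protocol 8.1 remains the only one stated.

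**Working it through.** The plan gives no expected rate, denominator or sample size for this endpoint, so there is no figure of its own to reproduce.

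**Inputs.** Planned evaluable numbers: 50 or 100 per cohort (Protocol Table 1; cohorts 1 and 2 share 100) and about 500 in total (Protocol 3). Interval: Wilson 95% (SAP 8.1.2), z² = 3.8415.

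**1. As written, numerator equal to denominator.** With x = n, the Wilson upper limit is 1 and the lower limit reduces to n/(n + z²):
- n = 50: 50/53.8415 = 92.9%
- n = 100: 100/103.8415 = 96.3%
- n = 500: 500/503.8415 = 99.2%

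The estimate is 100% each time, whatever the true yield.

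**2. If *fully* is stricter than *sufficient*.** The endpoint refers to every intended analysis at every time point; Protocol 8.1 is worded less strictly. Suppose 2 of 100 evaluable patients miss only the stricter condition (assumption). The result is 98/100 = 98.0% (93.0% to 99.4%). Those 2 count as failures, but patients whose pair failed basic sufficiency are still absent.

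**3. With failures in the denominator.** The documents give no yield, so these are illustrations for 100 adequate pairs:

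| Patients in denominator (assumed) | Rate | Wilson 95% CI |
|---|---|---|
| 103 | 97.1% | 91.8% to 99.0% |
| 107 | 93.5% | 87.1% to 96.8% |
| 125 | 80.0% | 72.1% to 86.1% |
| 200 | 50.0% | 43.1% to 56.9% |

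The first two intervals overlap the as-written 96.3% to 100%; the last two lie wholly below it.

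**4. Which denominator.** SAP 5.1 puts in the SA population any enrolled patient who had a de novo biopsy *or* a research blood draw. Blood may be taken up to 5 days before the biopsy (Protocol 5.2.1), so a patient can give blood and never have the biopsy. If 125 patients were biopsied and 10 more gave blood only (assumption), the SA rate is 100/135 = 74.1% (66.1% to 80.7%), against 80.0% among those biopsied. The 10 are failures to obtain a pair. On the natural reading of Protocol 5.1.2, where a screen failure has neither procedure, they are not screen failures either. A biopsied-only denominator would lose them from both counts.

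**The case against.** The strongest reply is that the SAP has moved on from Protocol 8.1. SAP 5 replaces the single evaluable population with several. BE (TBD), used for concordance, does not require paired tissue. The fully biomarker evaluable (FBE) population is defined as a subset of SA, and no other visible analysis has an evident use for it. The ratio FBE/SA would then be the intended rate, and SAP 8.4 already promises the size of each population by cohort.

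This is a plausible account of intent, but it remains an inference. No visible sentence assigns FBE or SA to this endpoint, parts of the SAP are blacked out, and SAP 8.4 promises counts, not this rate. FBE also measures something else: it requires every biomarker result, and SAP 7.1 lists blood cfDNA among the biomarkers. A failed blood assay could therefore exclude a patient whose tissue pair was adequate.

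Three parts of the reply stand. The explanation of *fully evaluable* is introduced as an example, so exactly 100% is not certain. The assay list in SAP 7.1 is open-ended, so a sufficiency numerator needs the tissue assays named. And Protocol 8 demands an amendment only for major changes to the primary endpoint or its analysis, so a SAP statement is enough for now.

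**Conclusion.** The point holds. The only population rule stated for this endpoint gives 100%, or slightly less on the stricter reading of *fully*, and in both cases leaves out the pairs that failed basic sufficiency. The stated objective is not met. This is a wrong rule for one endpoint, not merely a missing detail, and it should be fixed.

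The size in practice is unknown. Every rate below 100% shown above is an assumption, and at high yield the reported figure would differ little from the true one.

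A reader might infer more than the documents support:
- *The trial will report 100%.* Not established: *fully* may be stricter, and the team may in fact compute FBE/SA.
- *The plan conceals a poor yield.* No yield is given in either document.
- *The primary result is compromised.* It is a within-pair change, which needs both samples in any case, and it does not use this denominator. No formal hypothesis testing is planned under SAP 4.1 and no decision rule under SAP 4.2, so none hangs on this descriptive endpoint.

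**What to change.** In SAP 8.2.2, state that this endpoint is not analysed in the evaluable population, and define:
- **Numerator:** the endpoint's own condition, archival and de novo tissue both sufficient for all intended tissue analyses, with those assays named.
- **Denominator:** the existing SA population, so that a blood draw without a biopsy, or an inadequate biopsy, counts as a failure.
- **Reporting:** proportion and Wilson 95% CI by cohort. The rate among biopsied patients may be added as a supplementary figure.
- **Context:** a statement that the rate is conditional on archival tissue having passed the local screening check (Protocol 4.1, criterion 5; Protocol 5.1.3), with the number of screen failures alongside.

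Align the sentence in Protocol 8.1 at the next amendment.

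The cost is minor wording and a less favourable reported rate. SA counts by cohort are already planned (SAP 8.4), and screen failures are already recorded (Schedule of Activities, footnote 3; Protocol 5.1.4).
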